# Adjuvant blood collection will take place at follow-up visits (30d, 90d, 180d and 360d ( $\pm$ 14d) after surgery).

Adjuvant therapy such as systemic therapy +/- radiation therapy following surgery will be administered according to the standard of care per judgment of the treating physician(s).

### 3.0 OBJECTIVES & HYPOTHESES

#### 3.1 Primary Objectives & Hypotheses

(1) **Objective:** To determine the change in the number of infiltrating CD3+ T cells/  $\mu\text{m}^2$  in the lung cancer tissue between the paired biopsy and thoracotomy specimens, as quantified by immunohistochemistry (IHC) and image analysis.

**Hypothesis:** For resectable NSCLC, the administration of pembrolizumab +/- low-dose stereotactic SRT in the preoperative window will enhance tumor immunogenicity, resulting in two-fold greater infiltrating CD3+ T cells/  $\mu\text{m}^2$  in the primary and/or regional environment at the time of surgical resection, as compared to the time of initial biopsy.

#### 3.2 Secondary Objectives & Hypotheses

(1) **Objective:** To assess the safety of preoperative pembrolizumab +/- SRT when combined with surgery;

**Hypothesis:** In patients scheduled for NSCLC resection, pembrolizumab, or pembrolizumab + SRT, given in the preoperative window, will meet safety criteria described by the protocol;

(2) **Objective:** To record the toxicity of preoperative pembrolizumab +/- SRT when combined with surgery, according to CTCAE v. 4, including immune-related adverse events (AEs);

**Hypothesis:** In patients scheduled for NSCLC resection, pembrolizumab, or pembrolizumab + SRT, given in the preoperative window, will result in acceptable short-term and perioperative toxicity;

(3) **Objective:** To determine the 1-year overall survival rate resulting from preoperative pembrolizumab +/- SRT when combined with surgery;

**Hypothesis:** In patients scheduled for NSCLC resection, pembrolizumab + SRT given in the preoperative window will result in a higher 1-year survival rate than pembrolizumab alone;

(4) **Objective:** To determine the 1-year relapse free survival rate resulting from preoperative pembrolizumab +/- SRT when combined with surgery;

**Hypothesis:** In patients scheduled for NSCLC resection, pembrolizumab + SRT given in the preoperative window will result in a higher 1-year relapse free survival rate than pembrolizumab alone;

(5) **Objective:** To determine the 1-year rate of distant metastases resulting from preoperative pembrolizumab +/- SRT when combined with surgery;

**Hypothesis:** In patients scheduled for NSCLC resection, pembrolizumab + SRT given in the preoperative window will result in a lower 1-year distant metastasis rate than pembrolizumab alone;

(6) **Objective:** To assess quality of life associated with preoperative pembrolizumab +/- SRT when combined with surgery;

**Hypothesis:** In patients scheduled for NSCLC resection, pembrolizumab, or pembrolizumab + SRT, given in the preoperative window, will result in acceptable short-term and perioperative quality of life;

(7) **Objective:** To determine the rate of unresectability that results from a program of preoperative pembrolizumab +/- SRT to be followed by a planned surgery;

**Hypothesis:** In patients scheduled for NSCLC resection, either pembrolizumab or pembrolizumab + SRT given in the preoperative window will both result in <15% overall rate of unresectability following the preoperative program;

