## 2.0 TRIAL DESIGN

### 2.1 Trial Design

This is a randomized single-institution, phase II, open-label clinical trial of neoadjuvant pembrolizumab with or without low-dose stereotactic radiation therapy (SRT) in stage I- IIIA non-small lung cancer (NSCLC) patients who are planned to undergo surgical resection of their lung cancer.

Two consecutive run-in cohorts will administer pembrolizumab or pembrolizumab with SRT of 12 Gy to the lateral aspect of the primary tumor. Patients will receive pembrolizumab for 2 cycles prior to surgery or SRT and surgery. Surgical resection of all involved areas of tumor will occur within 6 weeks of the last administration of pembrolizumab. It should be noted that in almost all cases, surgery is expected to occur very expeditiously, within a much shorter window and 6 weeks would represent only the greatest allowable amount of delay.

If during the run-in, only the pembrolizumab-alone cohort meets pre-specified safety parameters, subsequently enrolled patients will enter a larger expansion cohort, with treatment given according to that cohort only. If during the run-in both cohorts meet pre-specified safety parameters, subsequently enrolled patients will enter the expansion cohort and be randomized between preoperative pembrolizumab versus pembrolizumab with SRT of 12 Gy.

Patients will be followed every 12 weeks for 1 year for disease status and survival.

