**Expansion Cohort:** 28 patients. The patients will be treated according to Cohort 1 if Cohort 2 failed to meet the specified safety milestones. If both cohorts met the safety milestones, then patients in this cohort will be randomized to parameters of either Cohort 1 or Cohort 2. Surgery will occur no later than 6 weeks following the last dose of pembrolizumab.

**Stopping Rule:** If at any point during the study, >15% of patients progress to unresectability over the course of the study treatment, then the study will terminate. This stopping rule will be cumulatively evaluated at all timepoints during the protocol, for all patients enrolled in any phase of the protocol. Each case of study-induced medical unfitness, tumor progression, or any other cause resulting in unresectability will trigger a re-evaluation of the 15% stopping rule.

\* Cycle 2 of pembrolizumab should be given except as recommended per protocol, section 5.2.1.2

\*\* SRT is delivered within 7 days +/- 3 days of second pembrolizumab cycle. If second cycle is not given due to discontinuation, SRT should not be given (patient should continue to surgery)

when deemed safe by treating surgeon).

^ Surgery will take place no later than 6 weeks following last dose of pembrolizumab, e.g. no later than week 7 if only one cycle of pembrolizumab was tolerated, or if two cycles of pembrolizumab were given, week 10.

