#### **4.2 PD-L1 expression by immunohistochemistry**

Pembrolizumab has been approved for use with a companion diagnostic, the PD-L1 immunohistochemistry (IHC) 22C3 pharmDx test, the first test designed to detect PD-L1 expression in NSCLC. The clinical trial assay was developed by Dako, an *in vitro* diagnostic manufacturer. In the KEYNOTE-001 trial, the overall prevalence of PD-L1 expression  $\geq 1\%$  was 60.8% among 824 patients including 58.6% of the 643 previously treated patients and 68.5% of the 181 previously untreated patients. The prevalence of a proportion score (PS) of at least 50% was 24.9% among previously untreated patients and 22.7% among previously treated patients (Garon 2015). Notably, the ORR (45.2% vs. 16.5% vs. 10.7%), PFS (6.4 vs. 4.1 vs. 4.0 months), and OS (not reached vs. 10.6 vs. 10.4 months) were significantly higher for patients whose tumors expressed PD-L1 membranous staining  $\geq 50\%$  compared to patients with a PS of 1–49% or those with a score less than 1%. A cutoff of  $\geq 50\%$  PD-L1 positivity in tumor cell membranes was determined as optimal by receiver operating characteristic (ROC) analysis. In contrast, PD-L1 expression was not associated with predictive markers of any efficacy endpoints in the Checkmate 017 study with nivolumab, in which patients with pretreated squamous NSCLC were compared with those treated with docetaxel (Brahmer 2015). There was a favorable trend of unstratified hazard ratios toward nivolumab in patients with higher PD-L1 expression ( $\geq 10\%$ ,  $\geq 5\%$ , and  $\geq 1\%$ ) and similar rates of objective response were observed among patients with PD-L1 positive tumors and those with PD-L1 negative tumors. On the other hand, another trial of nivolumab in pretreated advanced non-squamous NSCLC (Checkmate 057) compared with docetaxel demonstrated a meaningful separation of the overall survival curves across all pre-specified PD-L1 expression levels (at  $\geq 1\%$ ,  $\geq 5\%$ , and  $\geq 10\%$ ) (Borghaei 2015). However, PD-L1 expression in both studies was evaluated retrospectively in pretreatment (archival or recent) tumor biopsy specimens using rabbit monoclonal antihuman PD-L1 antibody (clone 28-8, Epitomics). In a phase I study of anti-PD-L1 antibody MPDL3280A, PD-L1 was stained with an antihuman PD-L1 rabbit monoclonal antibody (clone SP142, Ventana) and PD-L1 expression was evaluated on both tumor cells and tumor-infiltrating immune cells. While the association of response to MPDL3280A treatment and tumor-infiltrating immune (TIL) cell PD-L1 expression was significant, the association with tumor cell PD-L1 expression was not (Herbst 2014).

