#### **4.4 Secondary Objectives & Hypotheses**

Secondary objectives include safety according to criteria described by the protocol ( $\leq 33\%$  grade 3 immune-related toxicity); toxicity according to CTCAE v. 4, including immune-related adverse events (AEs); and quality of life.

Other secondary objectives include the 1-year overall survival rate, 1-year relapse free survival, 1 year rate of distant metastases, and rate of progression to unresectability following the preoperative program. These exploratory data will provide an initial basis for investigating which of these two programs might provide the best overall clinical benefits and merit further study.

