#### **4.5 Exploratory Objectives**

##### 4.5.1 Biomarker Research

PD-L1 expression will be tested in tumor specimens to investigate correlations to immune response from treatment with pembrolizumab.

Other exploratory objectives will further describe immune changes resulting from neoadjuvant pembrolizumab +/- SRT. These will include: changes in the number of infiltrating T cell subsets; change in the intratumoral T-cell repertoire by TCR sequencing and single-cell T-cell profiling; and treatment-induced changes in the circulating T cell immune response using TCR sequencing and enzyme-linked immunospot (ELISPOT) assays.

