### **5.4 Stratification**

No stratification is to be performed.

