#### 7.2 Statistical Analysis Plan

Sample size justification:

The sample size is based upon the anticipated number of patients who will have samples that will be useful for study of immunologic changes in the number of infiltrating CD3+ T cells/ $\mu\text{m}^2$  in the lung cancer tissue between the pre-treatment (baseline) biopsy and post-treatment thoracotomy specimens.

The sample size is fixed at 40 patients. It assumes successful accrual of 6 patients from each of the two run-in cohorts and an additional 28 patients from the randomized expansion cohort, for a total of 40 patients. However, past clinical experience indicates that as many as one-third of patients may not be able to complete a new successful core needle biopsy procedure and only prior archived tissues will be available for any analysis (which may eventually turn out to be insufficient to evaluate for primary endpoint). These patients who enrolled but whose core biopsy is later found to be inadequate after initiation of therapy will be allowed to continue on the protocol but will not be included in the primary endpoint.

The null hypothesis is that a two-fold increase will be seen in 15% of the evaluable 26 patients (assuming up to one third of samples may be unevaluable for primary endpoint). The alternative hypothesis is that a two-fold increase will be seen in 40% of the evaluable 26 patients. This yields 90% statistical power, with one sided 5% alpha level based on an exact binomial test.

The goal of achieving a two-fold increase in 40% of the evaluable population is a reasonable one, as estimated from a previous study showing greater-than-three-fold increase in 57% of patients when CD3+ T cells/ $\mu\text{m}^2$  were measured in prostate cancer tissue treated with a cell- based cancer immunotherapy, with a null hypothesis having been set at a two-fold increase in 15% of the population (Fong 2014). The current study includes immunotherapy +/- stereotactic radiation therapy, both of which are anticipated to create increased immunogenicity against NSCLC.

It is anticipated that accrual will be completed in 10 months (4 patients per month), with each patient treated for approximately 2.5-3 months and then followed for 12 months after completing protocol therapy. Total study duration is 25 months.

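### The SRT-versus-alone comparison in hypotheses 3 to 5 has no planned estimate, no stage stratification and no stage adjustment, so in about 28 patients a chance stage imbalance would go uncorrected

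*Combined protocol and SAP*

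**What the plan says.** Section 3.2, items 3 to 5, sets directional between-regimen hypotheses for three 1-year outcomes. Item 4 reads: "pembrolizumab + SRT given in the preoperative window will result in a higher 1-year relapse free survival rate than pembrolizumab alone". Section 4.4 calls these outcomes exploratory and describes them as an "initial basis for investigating which of these two programs might provide the best overall clinical benefits and merit further study".

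The population is defined in section 2.1 as "in stage I- IIIA non-small lung cancer (NSCLC) patients who are planned to undergo surgical resection of their lung cancer". Section 5.1.1 takes stage from PET-CT and does not require a mediastinal biopsy, so the stage known at entry is radiographic.

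Randomisation is conditional. Section 2.2 says: "If both cohorts met the safety milestones, then patients in this cohort will be randomized to parameters of either Cohort 1 or Cohort 2". Section 5.3 uses permuted blocks of 4 without stating the allocation ratio, and section 5.4 says: "No stratification is to be performed". On the sample size, section 7.2 says: "It assumes successful accrual of 6 patients from each of the two run-in cohorts and an additional 28 patients from the randomized expansion cohort".

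The only analysis in section 7.2 is a one-sample exact binomial test of the CD3+ endpoint against 15%. For items 3 to 5 there is no test, estimate, interval, analysis set or covariate. On PD-L1, section 4.5.1 says only: "PD-L1 expression will be tested in tumor specimens to investigate correlations to immune response from treatment with pembrolizumab".

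**The concern.** Resectable disease from stage I to IIIA covers patients who can be expected to relapse at different rates. With roughly 14 patients per arm, a few extra higher-stage patients on one side is an ordinary outcome of unstratified randomisation. If the arms are then compared crudely, part of any apparent SRT effect on relapse, metastasis or survival may be a stage difference.

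Screening stage is collected for everyone before treatment, so the plan could deal with this at little cost but does not. Because no between-arm analysis is written down at all, any adjustment would have to be chosen after the data are seen. What is at stake is the first indication of which regimen deserves further study. The primary endpoint, a one-sample test, is not affected by imbalance between arms.

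**Working it through.** **Plan's own figure.** There is none to reproduce. The documents give no sample size, power or effect size for SRT versus alone. The 26 evaluable patients and 90% power in section 7.2 belong to the CD3+ test.

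**Inputs from the documents.** 28 randomised, blocks of 4 (sections 2.2, 5.3); no stratification (5.4); stage I to IIIA (5.1.1).

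**Assumptions, not in the documents.** Allocation 1:1, so 28/4 = 7 full blocks and 14 v 14. Stage II-IIIA prevalence 30% to 50%. A gap of 20 to 40 points in 1-year relapse between stage I and stage II-IIIA. No true SRT effect.

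**Step 1: how often the arms differ.** The stage II-IIIA counts in the two arms are independent binomials with n = 14.

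| Prevalence | Differ by 3 or more | Differ by 4 or more | 4 or more, in SRT's favour (half) |
|---|---|---|---|
| 30% | 30.1% | 14.7% | 7.3% |
| 40% | 33.5% | 17.6% | 8.8% |
| 50% | 34.5% | 18.5% | 9.2% |

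Simulation of the permuted blocks agrees (14.7%, 17.3%, 18.2% for 4 or more). With blocks of 4 stratified by stage the difference cannot exceed 2 patients.

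**Step 2: size of the shift.** Shift = (imbalance / 14) x stage gap.
- 4 patients: (4/14) x 20 = 5.7 points; (4/14) x 40 = 11.4 points.
- Stratified maximum of 2 patients: (2/14) x 20 = 2.9 points; (2/14) x 40 = 5.7 points.

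**Step 3: compared with sampling noise.** Take equal stage groups. Crude SE = sqrt(2p(1-p)/14), where p is the overall risk. Within-stage SE = sqrt(2w/14), where w is the mean within-stage variance.
- Relapse 10% v 30%: p = 0.20, crude SE = sqrt(0.32/14) = 0.151; w = (0.09 + 0.21)/2 = 0.15, within-stage SE = sqrt(0.30/14) = 0.146.
- Relapse 5% v 45%: p = 0.25, crude SE = sqrt(0.375/14) = 0.164; w = (0.0475 + 0.2475)/2 = 0.1475, within-stage SE = sqrt(0.295/14) = 0.145.

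**Step 4: error rates.** Simulated with a factor of 25% to 40% prevalence and a 20 to 30 point gap in 1-year relapse-free survival, a crude one-sided 5% test has an overall false-positive rate of 4.6% to 5.7%. Among trials where the imbalance favours SRT by 20 points or more (at least 3 patients), it is about 9% to 14%. A Mantel-Haenszel test by the factor brings it back to about 5%.

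**Step 5: what adjustment buys overall.** In the two scenarios of step 3, the chance that SRT looks better by 20 points or more with no true effect falls from about 11% to 14% (crude) to about 9% (stage-adjusted).

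**Step 6: if the run-in patients are pooled.** The arms become 20 v 20. At 25% to 40% prevalence, an imbalance of 20 points or more still occurs in 20% to 26% of trials. The 12 added patients were enrolled sequentially, not randomised, so pooling adds a possible systematic difference.

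**The case against.** The strongest reply is that randomisation already protects the comparison on average, and that noise at this size swamps any stage shift. Both parts stand: overall type I error is near 5%, the standard error of about 15 points exceeds the 6 to 11 point shift, and most false wins remain after adjustment. Section 4.4 also labels the outcomes exploratory, and no selection rule or arm test depends on them. What survives is narrower: given an imbalance in the one trial actually run, the crude estimate is off in a known direction, and a baseline value already in hand would correct it. A second fair point is that leaving seven full blocks unstratified guarantees 14:14 under 1:1 allocation, which two strata do not.

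A reader might also infer four stronger things that the documents do not support.
- *That these data decide which program is taken forward.* Section 4.4 claims only an initial basis for investigating that.
- *That screening stage drives postoperative treatment.* Section 4.3.1 refers to surgical and pathologic stage, known only after treatment and resection.
- *That PD-L1 imbalance moves these outcomes by a calculable amount.* Section 4.2 reports strong separation by PD-L1, "the ORR (45.2% vs. 16.5% vs. 10.7%), PFS (6.4 vs. 4.1 vs. 4.0 months), and OS (not reached vs. 10.6 vs. 10.4 months", but in advanced disease. A shift computed from those response rates does not carry over to 1-year survival, relapse or metastasis after resection. Section 4.5.1 does not say that testing is pre-treatment, the flow chart has no PD-L1 row, and section 7.2 allows that up to a third of patients may have only archived, possibly insufficient, tissue.
- *That the 15% to 18% is the chance of a bias towards SRT.* It counts both directions.

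**Conclusion.** The point holds as a modest, inexpensive improvement to a secondary comparison. The plan states directional between-arm hypotheses in a stage-mixed population, forgoes stratification, and specifies neither a between-arm estimate nor a stage adjustment. An imbalance of four or more stage II-IIIA patients is expected in 15% to 18% of trials, 7% to 9% in SRT's favour, and would shift the crude 1-year relapse difference by 6 to 11 points.

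The frequencies rest on 1:1 allocation and an assumed 30% to 50% prevalence of stage II-IIIA; the shift rests on an assumed 20 to 40 point stage gap. The documents give none of these. Unconditional error is not inflated; the harm is conditional on the imbalance observed. Nor does the fix make the comparison informative: at 14 v 14, power to separate 75% from 90% relapse-free survival is 27% one-sided, and 80% power would need 79 per arm.

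**What to change.** 1. **Section 7.2.** For hypotheses 3 to 5, define the analysis set as the randomised patients only, and report each arm difference as a descriptive estimate with a confidence interval, adjusted for screening clinical stage (I versus II-IIIA), for example as a Mantel-Haenszel risk difference. Describe the run-in patients separately.
2. **Sections 5.3 and 5.4, if randomisation is not complete.** State the allocation ratio and stratify the permuted blocks by that one binary factor. More than one factor is hardly feasible with 28 patients.
3. **Reporting.** Tabulate stage by arm, and PD-L1 by arm where a pre-treatment sample allows. Any estimate that uses PD-L1 should be supportive only.

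The cost is two randomisation lists instead of one and a few lines of SAP text, with no extra patients, tests or visits. The downside of stratifying is incomplete last blocks: up to 2 patients of arm imbalance per stratum, so at worst 12:16 overall. If randomisation is already complete, items 1 and 3 still apply.

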### 3.3 Exploratory Objectives

(1) **Objective:** To determine the difference in the number of infiltrating T cell subsets (cytotoxic CD8+, helper CD4+ FOXP3-, and regulatory CD4+ FOXP3+ T cells) between the biopsy and the surgery specimens, as quantified by IHC and image analysis;

**Hypothesis:** Preoperative pembrolizumab +/- SRT will produce quantitatively detectable changes in the infiltrating T cell subsets as compared to pre-treatment biopsy;

(2) **Objective:** To determine the change in the intratumoral T-cell repertoire by TCR sequencing and single-cell T-cell profiling;

**Hypothesis:** Preoperative pembrolizumab +/- SRT will produce quantitatively detectable changes in the intratumoral T-cell repertoire as compared to pre-treatment specimens;

(3) **Objective:** To quantify treatment-induced changes in the circulating T cell immune response using TCR sequencing and enzyme-linked immunospot (ELISPOT) assays;

**Hypothesis:** Preoperative pembrolizumab +/- SRT will produce quantitatively detectable changes in the circulating T cell immune response as compared to pre-treatment specimens;

## 4.0 BACKGROUND & RATIONALE

### 4.1 Background

Refer to the Investigator's Brochure (IB)/approved labeling for detailed background information on MK-3475.

#### 4.1.1 Pharmaceutical and Therapeutic Background

The importance of intact immune surveillance in controlling outgrowth of neoplastic transformation has been known for decades. Accumulating evidence shows a correlation between tumor-infiltrating lymphocytes (TILs) in cancer tissue and favorable prognosis in various malignancies. In particular, the presence of CD8+ T-cells and the ratio of CD8+ effector T-cells / FoxP3+ regulatory T-cells seems to correlate with improved prognosis and long-term survival in many solid tumors.

The PD-1 receptor-ligand interaction is a major pathway hijacked by tumors to suppress immune control. The normal function of PD-1, expressed on the cell surface of activated T-cells under healthy conditions, is to down-modulate unwanted or excessive immune responses, including autoimmune reactions. PD-1 (encoded by the gene *Pdcd1*) is an Ig superfamily member related to CD28 and CTLA-4 which has been shown to negatively regulate antigen receptor signaling upon engagement of its ligands (PD-L1 and/or PD-L2). The structure of murine PD-1 has been resolved. PD-1 and family members are type I transmembrane glycoproteins containing an Ig Variable-type (V-type) domain responsible for ligand binding and a cytoplasmic tail which is responsible for the binding of signaling molecules. The cytoplasmic tail of PD-1 contains 2 tyrosine-based signaling motifs, an immunoreceptor tyrosine-based inhibition motif (ITIM) and an immunoreceptor tyrosine-based switch motif (ITSM). Following T-cell stimulation, PD-1 recruits the tyrosine phosphatases SHP-1 and SHP-2 to the ITSM motif within its cytoplasmic tail, leading to the dephosphorylation of effector molecules such as CD3, PKC $\theta$  and ZAP70 which are involved in the CD3 T-cell signaling cascade. The mechanism by which PD-1 down modulates T-cell responses is similar to, but distinct from that of CTLA-4 as both molecules regulate an overlapping set of signaling proteins. PD-1 was shown to be expressed on activated lymphocytes including peripheral CD4+ and CD8+ T-cells, B-cells, Tregs and Natural Killer cells. Expression has also been shown during thymic development on CD4-CD8- (double negative) T-cells as well as subsets of macrophages and dendritic cells. The ligands for PD-1 (PD-L1 and PD-L2) are constitutively expressed or can be induced in a variety of cell types, including non-hematopoietic tissues as well as in various tumors. Both ligands are type I transmembrane receptors containing both IgV- and IgC-like domains in the extracellular region and contain short cytoplasmic regions with no known signaling motifs. Binding of either PD-1 ligand to PD-1 inhibits T-cell activation triggered through the T-cell receptor. PD-L1 is expressed at low levels on various non-hematopoietic tissues, most notably on vascular endothelium, whereas PD-L2 protein is only detectably expressed on antigen-presenting cells found in lymphoid tissue or chronic inflammatory environments. PD-L2 is thought to control immune T-cell activation in lymphoid organs, whereas PD-L1 serves to dampen

unwarranted T-cell function in peripheral tissues. Although healthy organs express little (if any) PD-L1, a variety of cancers were demonstrated to express abundant levels of this T-cell inhibitor. PD-1 has been suggested to regulate tumor-specific T-cell expansion in subjects with melanoma (MEL). This suggests that the PD-1/PD-L1 pathway plays a critical role in tumor immune evasion and should be considered as an attractive target for therapeutic intervention.

Pembrolizumab is a potent and highly selective humanized monoclonal antibody (mAb) of the IgG4/kappa isotype designed to directly block the interaction between PD-1 and its ligands, PD-L1 and PD-L2. KeytrudatTM (pembrolizumab) has recently been approved in the United States for the treatment of patients with unresectable or metastatic melanoma and disease progression following ipilimumab and, if BRAF V600 mutation positive, a BRAF inhibitor.

